4.3.2. Part 2: Open-Label, Randomized

Part 2 is an efficacy cohort where subjects are randomized to receive Arm A or Arm B as follows:

Arm A:

[figure not shown]
Treatment consists of the combination of plamotamab, tafasitamab, and lenalidomide administered in 28-day cycles, with 2 priming doses of tafasitamab before Cycle 1. Plamotamab and tafasitamab can be administered until disease progression, unacceptable toxicity, or discontinuation for any other reason, whichever comes first. Lenalidomide can be given for up to a total of 12 cycles.

Arm B:

Treatment consists of the combination of tafasitamab and lenalidomide administered in 28-day cycles with 2 priming doses of tafasitamab before Cycle 1. Tafasitamab can be administered until disease progression, unacceptable toxicity, or discontinuation for any other reason, whichever comes first. Lenalidomide can be given for up to a total of 12 cycles.

Part 1 and Part 2 dose and schedule are presented in the schematic below ([Figure 2](#)):

Figure 2: Dosing Schema

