11.3. Sample Size and Power

11.3.1. Progression-Free Survival

PFS as assessed by the BIRC is the primary endpoint for Part 2 of this study. For determination of the sample size, it is assumed that triple combination treatment could improve the median PFS from 12 months (under treatment with tafasitamab + lenalidomide (Duell, 2021) to 23.5 months under the triple combination treatment (plamotamab + tafasitamab + lenalidomide), corresponding to a hazard ratio (HR) of 0.51 with all randomized subjects (it is estimated that 90% of subjects will be central pathologically confirmed as DLBCL).

The log rank test has 90% power with the sample size of 200 (93 events) to preserve the type-I error of 0.025 (one-sided). A loss to follow-up rate of 1.5%/month was assumed for sample size calculations.

Subjects will be randomized 1:1, stratified by IPI risk score at baseline (3 to 5 versus 0 to 2), number of lines of prior therapy (1 versus ≥ 2), and primary refractory (yes versus no). A maximum of 36 primary refractory subjects may be enrolled into the sample size of 200.

Enrollment of 200 subjects is estimated to require 27 months with minimum follow-up time of 6 months. The primary efficacy analysis will occur when 93 PFS events per independent review have been observed. Efficacy boundaries and estimated timing for the analysis is displayed in [Table 21](#).

Table 21: Efficacy Boundaries and Properties for Progression-Free Survival Analyses

Analysis	Value	Efficacy
Final	Z	1.9600
N: 200	p (1-sided)	0.0250
Events: 93	HR at bound	0.6659
Month: 33	P(Cross) if HR = 1	0.0250
	P(Cross) if HR = 0.51	0.9000

p (1-sided) is the nominal α for testing.

HR at bound is the approximate HR required to reach an efficacy bound

P(Cross if HR = 1) is the probability of crossing a bound under the null hypothesis

P(Cross if HR = 0.5) is the probability of crossing a bound under the alternative hypothesis

HR = hazard ratio.

An interim analysis for OS at the time of final PFS analysis will be implemented using the group sequential design in addition to the final OS analysis. [Table 22](#) provides the timing of PFS and OS analysis.

Table 22: Summary of Interim and Final Analyses Strategy

Analyses	Key Endpoints	Timing	Estimated Time after First Subject Randomized	Primary Purpose of Analysis

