11.8. Safety Analysis

Safety Analysis will be performed with Safety Analysis Set. Safety variables will include AEs/SAEs, vital signs, PE findings, ECGs, laboratory values, medical history, and concomitant medications, which will be summarized by Part and by Arm.

The extent of exposure to plamotamab and tafasitamab will be summarized based on the number of infusions administered and the number of treatment cycles completed, as well as the total dose received. Lenalidomide exposure will be summarized similarly, based on number of doses taken.

Additional summaries of drug exposure will be provided based on the PK parameters described in [Section 11.10](#).

AEs will be coded using the latest version of Medical Dictionary for Regulatory Activities (MedDRA). The verbatim term recorded by the Investigator will be mapped to System Organ Class (SOC) and Preferred Term using MedDRA.

TEAEs are defined as events with onset dates on or after the start of study treatment or events that are present before the first infusion of study treatment and subsequently worsen in severity.

AE-related endpoints include:

- Treatment-emergent AEs
- Treatment-emergent SAEs
- Adverse reactions
- Serious adverse reactions
- Treatment-emergent AEs by severity, as defined by NCI-CTCAE Version 5.0
- Treatment-emergent AEs resulting in the permanent discontinuation of plamotamab

All AE-related endpoints will be summarized by SOC and preferred term. At each level of summation, subjects will be counted once, under the greatest severity and strongest study-drug relationship.

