The hematology, chemistry, and other laboratory values and change from baseline values will be summarized descriptively for each scheduled assessment time point and grouped by dosing cohort. The baseline value for each laboratory value is defined as the last assessment performed on or prior to the date of first dose of study treatment. The frequencies of Grade 3 and 4 hematologic AEs (including neutropenia, thrombocytopenia, and anemia) will be reported. The toxicity grades for laboratory tests will be based on NCI-CTCAE Version 5.0 ([NCI-CTCAE, 2017](#)) criteria. The use of blood transfusions (platelets, RBCs) and/or growth factor support will be reported. Similar analyses will be done for chemistry tests (including liver and renal function tests). Subject listings of all laboratory data collected during the study will be presented. Laboratory values outside normal limits will be identified in the subject listings and will include flags for high and low values.

Vital sign results (blood pressure, heart rate, respirations, temperature, and blood oxygen saturation by continuous pulse oximetry) will be summarized descriptively for each scheduled time point. The baseline value for each vital sign measurement is defined as the last assessment performed most recently prior to the first dose of study treatment, and any change from these baseline values will be reviewed. The change of vital signs values from preinfusion will be summarized for each postinfusion point. Preinfusion assessments are defined as last vital assessment prior to the same infusion. Subject listings of all vital data collected during the study will be presented.

ECGs values and change from baseline values will be summarized descriptively for each scheduled time point. Subject listings of all ECG data collected during the study will be presented.

Additional analysis will be performed for AEs of CRS. These will include analyses of time to onset, duration, severity, and associations with laboratory cytokine measurements and missed or delayed doses (ie, CRS may be associated with longer intervals between doses). Graphical summaries will illustrate the timing relative to dosing, the severity of CRS events and cytokine levels.

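### Part 2 adverse events would be compared between arms by crude subject incidence only, although time on treatment is expected to differ between arms

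*Protocol*

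**What the plan says.** Protocol Section 11.8 (Safety Analysis) summarizes safety variables by Part and by Arm, and adverse-event endpoints by system organ class and preferred term. At each level "subjects will be counted once, under the greatest severity and strongest study-drug relationship". The Synopsis repeats the rule. One endpoint in the list is "Treatment-emergent AEs by severity, as defined by NCI-CTCAE Version 5.0"; adverse reactions are a separate entry.

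Time and exposure enter in two other places. Section 11.8 states "The extent of exposure to plamotamab and tafasitamab will be summarized based on the number of infusions administered", together with cycles and total dose, but does not use exposure as a denominator for adverse events. For CRS it plans further analyses: "These will include analyses of time to onset, duration, severity, and associations with laboratory cytokine measurements". Section 4.2.2 also names timing for CRS and for neurological events (items 6 and 7).

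On treatment duration, Section 4.3.2 says for Arm A: "Plamotamab and tafasitamab can be administered until disease progression, unacceptable toxicity, or discontinuation for any other reason, whichever comes first". Arm B has the same stopping rule for tafasitamab. In both arms, "Lenalidomide can be given for up to a total of 12 cycles". Table 17 ends adverse-event reporting at 90 days after the last dose, at the start of another anticancer therapy, or at withdrawal of consent.

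Section 11.3.1 assumes that the triple combination will "improve the median PFS from 12 months" to 23.5 months. SAP Sections 1, 4.1 and 7 state that the study was terminated with 3 subjects enrolled and that only listings will be produced.

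**The concern.** A crude percentage answers how many subjects were ever affected while they were being watched. When treatment stops at progression, the length of watching is itself an outcome of treatment. If Arm A delays progression as hoped, its subjects spend longer at risk of every event that accrues over time, and its percentages rise even when the monthly risk is the same in both arms.

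This bears on a stated aim. The primary objective (Section 3.1) is to determine safety as well as efficacy compared with tafasitamab plus lenalidomide, and TEAE incidence and severity in Part 2 is a secondary endpoint (Section 4.2.2, item 9). A better efficacy result would make Arm A's crude safety figures look worse.

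A smaller issue lies in the counting sentence. It names two maxima, severity and relationship, without saying whether both must come from the same event. If they were crossed in one table, a subject with an unrelated Grade 4 event and a related Grade 1 event in the same system organ class could appear as a related Grade 4.

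**Working it through.** **Inputs from the protocol (Section 11.3.1).** Median PFS 12 months (B) and 23.5 months (A); 100 subjects per arm; 27 months' accrual, taken as uniform; primary analysis at month 33; loss to follow-up 1.5% per month. Month 51 is the final OS analysis (Table 22).

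**Assumptions of this check.** Exponential times. Time on treatment ends at progression, death or loss. The event rate μ is constant and identical in both arms; 2% and 5% per month are illustrative values, because the documents give none.

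**1. The plan's own figure.** With z-values 1.960 and 1.2816, the required events are 4 × (1.960 + 1.2816)² / (ln 0.51)² = 92.7, so 93 as stated. For timing, let λ = ln 2 / median and h = λ + 0.015:

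- Arm B: λ = 0.05776, h = 0.07276
- Arm A: λ = 0.02950, h = 0.04450

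Expected events per arm at month T are 100 × (λ/h) × [1 − (e^(−h(T−27)) − e^(−hT)) / (27h)]. At T = 33 this gives 56.93 + 36.75 = 93.7. The model reproduces the design.

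**2. Mean time on treatment.** (1/h) × [1 − (e^(−h(T−27)) − e^(−hT)) / (27h)].

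- Month 33: B 9.86, A 12.46 months; ratio 1.26
- Month 51: B 12.69, A 17.98 months; ratio 1.42

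The ratio at month 33 is far below 23.5/12 = 1.96 because accrual and cutoff truncate both arms.

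**3. Crude incidence on treatment.** With s = h + μ: (μ/s) × [1 − (e^(−s(T−27)) − e^(−sT)) / (27s)]. For μ = 0.02 and T = 33:

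- B: s = 0.09276; 0.2156 × [1 − (0.5732 − 0.0468)/2.5045] = 0.170
- A: s = 0.06450; 0.3101 × [1 − (0.6791 − 0.1190)/1.7415] = 0.210

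**4. Adding the 90-day window.** Allow 3 further months at risk after treatment ends, cut at the data cutoff. A subject with potential follow-up t then has event probability 1 − [(h/s)(1 − e^(−s(t−3))) e^(−3μ) + e^(−h(t−3)) e^(−μt)], averaged over t from T − 27 to T.

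| Month | Rate per month | On treatment only, B / A | Full 90-day window, B / A |
|---|---|---|---|
| 33 | 2% | 17.0% / 21.0% | 20.5% / 23.6% |
| 33 | 5% | 35.1% / 42.1% | 41.9% / 47.1% |
| 51 | 2% | 20.7% / 27.9% | 25.1% / 31.5% |
| 51 | 5% | 40.1% / 50.9% | 48.2% / 57.2% |

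If loss to follow-up also operates within the window, the month-33 figures become 19.7% / 22.7% and 40.4% / 45.3%, so the gaps barely change. The window narrows the month-33 gap from 4.0 to about 3 points at 2%, and from 7.0 to about 5 points at 5%. New anticancer therapy shortens the window, so the gap under this model lies between the two columns. In every row the true rate ratio is 1.00 by construction.

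**5. Where the effect is small.**

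- Events confined to the first 1, 2 or 3 months: 30% in Arm B becomes 30.4%, 30.8% or 31.2% in Arm A.
- Lenalidomide, capped at 12 cycles: mean exposure at month 33 is 7.35 (B) and 8.41 (A) months, a ratio of 1.14.
- Extra discontinuation of all treatment in Arm A of 0.05776 − 0.02950 = 0.0283, or about 2.8% per month, would remove the difference in exposure.

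**6. The counting rule.** The documents specify no severity-by-relationship table and give no numbers of events per subject, so no size can be derived.

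**The case against.** The strongest objection is practical. The SAP replaces the tables with listings for 3 subjects. Part 2 could open only after a safety evaluation of at least 40 Part 1 subjects (Section 4.1.2), so no comparison of Arm A with Arm B will be made. That stands, and it confines the point to the design as written.

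Second, crude incidence is a valid descriptive summary. Exposure is reported alongside it, CRS has its own timing analysis, and Part 2 TEAEs lie outside the testing sequence of Section 11.3.4. The primary safety endpoint belongs to single-arm Part 1, where no between-arm bias arises. All of this is true and lowers the weight of the point. But an exposure table beside crude percentages does not let a reader adjust event by event.

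Third, a reader might infer that Arm A's toxicity is inflated across the board. The documents do not support this. Longer treatment in Arm A is a consequence of the PFS hypothesis, not a documented fact. Early events barely move, and enough extra discontinuation in Arm A would reverse the direction. Sections 7.1.1 to 7.1.3 allow a subject to stop one drug and continue the others, which makes a full offset less likely but does not exclude it. If Arm A were treated for less time, crude figures would understate its risk, and the same remedy would apply.

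Fourth, a reader might infer that worst grade and strongest relationship are always combined from different events. Section 11.8 does not say so. Severity and adverse reactions are separate entries in its endpoint list, and two separate tables would mix nothing. The wording permits the combination but does not require it.

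**Conclusion.** The point holds for Part 2 as designed, in limited form. Section 11.8 gives no general adverse-event comparison that accounts for time at risk, while both arms are treated to progression. Under the plan's own PFS, accrual and loss assumptions, Arm A is treated about 26% longer at month 33. A constant-rate event with no true difference would then show an excess in Arm A of about 3 to 4 points at 2% per month and about 5 to 7 points at 5% per month. The ranges run from the full 90-day window to no window. The gaps are wider at month 51.

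These sizes rest on exponential times, a constant and equal event rate, and equal discontinuation for reasons other than progression. They do not apply to early events such as step-up CRS. The counting sentence is an ambiguity to be clarified, not a demonstrated bias. Nothing in the current SAP output changes.

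**What to change.** If Part 2 is run or the text is reused, add to Section 11.8 and the SAP, beside the crude percentages, one of these by arm:

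- exposure-adjusted incidence: subjects with a first event per 100 patient-months at risk, counting time to the first event, the end of the 90-day window or the data cutoff; or
- cumulative incidence at Cycle 6 and Cycle 12, stating how death and the end of the reporting window are handled. This option does not need a constant rate.

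As a secondary clarification, state that worst grade and strongest relationship are tabulated separately, and that any severity-by-relationship table selects related events first and then takes the worst grade.

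The cost is a few extra tables. Event dates, grades, causality and dosing records are already to be collected under Sections 7.3, 7.11, 10.2.3 and 10.3. For the 3 enrolled subjects no change is needed.

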11.9. Efficacy Analysis

The Randomized (intent-to-treat) Analysis Set defined in [Section 11.5](#) will be used for primary and secondary efficacy analyses, unless otherwise noted. Sensitivity analyses will be provided based on

pathologically confirmed DLBCL. Strata might be combined for the analysis if randomization resulted in sparse stratum. The decision to combine strata will be made prior to the database lock.

The primary analysis will be based on PFS as assessed by the BIRC, defined as the time from randomization to first documentation of progressive disease or death, whichever comes first. Subjects who discontinue the study without progression as assessed by BIRC will be censored according to rules specified in the SAP. Kaplan-Meier methodology will be used to summarize the distribution of PFS, presenting median survival together with its 95% confidence intervals and PFS curves for each treatment arm. The primary inferential comparison between treatment groups will use the log-rank test stratified by the randomization stratification factors listing in [Section 11.6](#). The HR for triple combination treatment versus control and its 95% confidence intervals (CI) will be estimated using a Cox proportional hazards model stratified by the same randomization stratification factors. For the secondary endpoint of PFS as assessed by the Investigator, analyses will be similar to the primary analysis. In addition, the SAP will detail a tipping-point sensitivity analysis of potential impacts of informative censoring among subjects who discontinue the study early without progression as assessed by BIRC (ie, not including on-study subjects administratively censored at the time of the analysis).

Analyses of response will be based on the rate of objective response (ORR = CRR + PRR) by BIRC per Lugano 2014 criteria ([Cheson, 2014](#)). By-arm comparisons will be made with a stratified Cochran-Mantel-Haenszel test using randomization stratification factors. In addition, response rates and Barnard's exact confidence intervals will be reported both overall and for the categorical Key Subgroups in [Section 11.6](#). The number and percentage of subjects achieving a best overall response of CR (confirmed and unconfirmed), PR (confirmed and unconfirmed), stable disease, progressive disease, not evaluable, and other disease-specific response criteria will be presented.

In addition to BIRC response assessments, Investigator-assessed responses will be reported similarly, and concordance analyses will be detailed in the SAP.

The duration of objective response will be calculated from the time of initial response (PR or better) to the first documentation of relapse (recurrence after CR), progression, or death. The duration of complete response will be calculated from the time of initial response (CR) to the first documentation of relapse (recurrence after CR), progression, or death among subjects achieving a CR.

Time to event analysis of OS, measured relative to randomization, will be performed based on the Kaplan-Meier method. Median survival time and its 95% confidence interval, as well as the 25th and 75th quartiles with their 95% confidence intervals, will be summarized. Subjects who are alive at end of the study will be censored at last known contact date. By-arm comparisons will utilize the same methods as for PFS.

The potential antitumor effects of plamotamab may be evaluated in subgroups of subjects, including the Key Subgroups defined in [Section 11.6](#). The specifications for these and other similar analyses will be described in the SAP, which supersedes any protocol specifications.

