11.3.3. Objective Response Rate

The one-sided α level for testing ORR is at 0.025. It is assumed the ORR for Part 2 Arm B is 60% and ORR for Part 2 Arm A is 78%. 100 subjects per arm will provide 80% power for statistical significance at 0.025.

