11.3.4. Statistical Testing Sequence

The following secondary endpoints will be tested sequentially in the following order, if the test for the primary endpoint is positive:

1. ORR by BIRC per Lugano 2014 criteria ([Cheson, 2014](#))
2. OS

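### ORR is tested with a stratified CMH test, but the only interval named is Barnard's, with its target unstated, and no stratified ORR effect estimate is planned

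*Protocol*

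**What the plan says.** Protocol section 11.9 sets the ORR test: "By-arm comparisons will be made with a stratified Cochran-Mantel-Haenszel test using randomization stratification factors". Its next sentence adds response rates with Barnard's "exact confidence intervals will be reported both overall and for the categorical Key Subgroups". It does not name the quantity that the interval covers. No common odds ratio, stratified risk difference or other stratified measure of the ORR effect appears.

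For PFS, the same section pairs the stratified log-rank test with a hazard ratio and 95% CI, "estimated using a Cox proportional hazards model stratified by the same randomization stratification factors". OS uses the same between-arm methods as PFS.

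ORR heads the list in section 11.3.4: "The following secondary endpoints will be tested sequentially in the following order, if the test for the primary endpoint is positive". The first item is "ORR by BIRC per Lugano 2014 criteria", followed by OS and TTF. Section 11.3.3 says that the one-sided "level for testing ORR is at 0.025", assumes 60% in Arm B and 78% in Arm A, and states that "100 subjects per arm will provide 80% power for statistical significance at 0.025".

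The SAP adds no ORR method. Its sections 1, 4.1 and 7 record early termination after 3 subjects, with listings only.

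**The concern.** Barnard's method is an unconditional exact procedure for two independent proportions in a single 2×2 table. Each way of reading the sentence leaves a gap.

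- **Interval for each arm's rate.** The sentence mentions response rates, so this reading is possible. But Barnard's method gives no one-sample interval, so a programmer would have to substitute another method, and the plan would contain no between-arm ORR estimate.
- **Interval for the between-arm difference.** This suits the method, but the interval then ignores the three factors that the test uses. It can include zero when the CMH test is significant, and it gives up the precision that stratification offers.

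At stake is how a formally tested endpoint is reported: a reader should get an effect estimate and an interval that belong to the test. PFS and OS have that; ORR does not.

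**Working it through.** **1. The plan's own figure.** Inputs from section 11.3.3: 0.60, 0.78, n = 100 per arm, one-sided α = 0.025.

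- Pooled: mean rate 0.69. SE under the null = √(2 × 0.69 × 0.31 / 100) = 0.0654. SE under the alternative = √(0.60 × 0.40/100 + 0.78 × 0.22/100) = 0.0642. Power = Φ[(0.18 − 1.96 × 0.0654)/0.0642] = Φ(0.81) = 79.0%.
- Unpooled: Φ(0.18/0.0642 − 1.96) = 80.1%.
- Exact power of the pooled chi-square: 79.6%.

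The stated 80% is reproduced.

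**2. Barnard's rule at 100 against 100.** With pooled-score ordering, maximised over the nuisance rate, the critical value is Z ≥ 1.994 (actual size 0.0248). Power is 78.5%. The interval is taken to include zero when this rule does not reject.

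**3. Test against interval.** Simulated trials of 200 subjects in 2 × 2 × 2 = 8 strata, allocated 1:1 within strata, with overall rates held at 60% and 78%. CMH was run without continuity correction at 1.96. Assumptions not in the documents: 50% IPI 3 to 5, 50% with two or more prior lines, independent factors, and the prognostic strengths. Primary refractory is set at its cap, 36/200 = 18%.

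Equal odds ratio per factor, 40,000 trials each:

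| Odds ratio per factor | CMH power | Barnard power | CMH significant, Barnard includes 0 | Reverse |
|---|---|---|---|---|
| 1 | 79.2% | 78.6% | 0.8% | 0.2% |
| 1.5 | 80.1% | 78.8% | 1.4% | 0.1% |
| 2 | 81.3% | 78.9% | 2.5% | 0.1% |
| 3 | 84.4% | 80.0% | 4.4% | 0.01% |
| 4 | 87.0% | 80.8% | 6.1% | under 0.01% |

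Unequal log-odds (IPI / prior lines / refractory):

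- moderate, −0.5/−0.4/−0.8: 2.1%
- strong, −1.0/−0.7/−1.3: 4.0%

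Repeat runs gave 1.9% and 3.9%. The 0.8% that remains with non-prognostic factors reflects mainly Barnard's slightly higher cut-off (1.994 against 1.96). Ignoring prognostic strata therefore accounts for about 2.1 − 0.8 = 1.3 points (moderate) and 4.0 − 0.8 = 3.2 points (strong).

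**4. The stratified alternative.** In stratum k, let x₁, x₀ be responders, n₁, n₀ the arm sizes, and N = n₁ + n₀.

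- Difference: δ = Σ[(x₁n₀ − x₀n₁)/N] / Σ[n₁n₀/N]
- Sato variance: (δΣP + ΣQ) / (Σ[n₁n₀/N])²
- P = [n₁²x₀ − n₀²x₁ + n₁n₀(n₀ − n₁)/2]/N²
- Q = [x₁(n₀ − x₀) + x₀(n₁ − x₁)]/(2N)

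In the same simulations the 95% interval for δ disagreed with CMH, in either direction, in about 0.7% of trials. Most of these were intervals excluding zero beside a non-significant CMH. With Greenland-Robins variance the figure was about 2.5%.

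The Sato standard error was about 0.98 (moderate) and 0.94 (strong) times the unstratified one. The unstratified interval is therefore 1/0.98 = 1.02 to 1/0.94 = 1.06 times as wide, before Barnard's higher cut-off is counted.

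**The case against.** The case against has four parts.

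- **No decision changes.** The CMH test alone decides ORR, and the sequence in section 11.3.4 runs on tests. A reader might infer that, because OS and TTF come after ORR, the interval choice weakens that gate. The documents do not support this: the interval plays no part in the sequence. This objection stands in full.
- **The contradiction is conditional.** A reader might infer that the plan's ORR interval contradicts its test. That is possible only if the interval is for the difference, which section 11.9 does not say. This stands, but the unstated target is itself a gap.
- **The size is easily overstated.** Figures of about 3% to 7% can be produced by fixing the odds ratio within strata. Arm A's overall rate then falls below the planned 78%; with strong strata the difference shrinks to about 16 points. Those figures do not describe the design in section 11.3.3.
- **A stratified interval is not a complete cure.** The Mantel-Haenszel interval does not use the CMH null variance. With Greenland-Robins variance (about 2.5%) it would do no better than Barnard under moderate strata. This stands, and it is why the variance must be named. With Sato variance the gain is clear when the strata are prognostic, and small when they are not.

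Protocol section 11.1 also leaves detailed methods to the SAP, so a full SAP could have closed the gap. The SAP as issued cancels the efficacy analyses instead.

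**Conclusion.** The point holds as a minor reporting gap in protocol section 11.9. The only ORR interval named is an unstratified two-sample method, its target is not stated, and ORR lacks the stratified effect estimate that PFS and OS have.

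If the interval is for the difference, it would include zero beside a significant CMH result in roughly 1% to 4% of trials at the planned rates, from non-prognostic to strong strata, and in about 6% at an odds ratio of 4 per factor. The loss of precision is about 2% to 6% in width for moderate to strong strata. These sizes rest on assumed prevalences and prognostic strengths. If per-arm intervals are meant, no such conflict arises, but the method does not fit and no between-arm estimate is planned.

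Type I error, the stated 80% power, the CMH decision and the testing sequence are untouched. With 3 subjects and listings only, no result of this trial is affected. The value lies in correcting the protocol text and any reuse of it.

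**What to change.** In section 11.9:

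- Name the Mantel-Haenszel stratum-weighted difference in ORR, with a 95% CI using Sato variance, as the effect estimate that accompanies the CMH test. Use the same strata as the test, including any pooling of sparse strata decided before database lock.
- Use Clopper-Pearson intervals for each arm's response rate.
- Keep unstratified exact intervals for the between-arm difference as supportive output in the Key Subgroups, and say that the difference is what they cover.

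The Sato form suits the sparse cells here: with at most 36 primary refractory subjects, the four refractory strata average no more than 36/4 = 9 subjects across both arms.

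The cost is a few lines of text and standard software. Sample size, data collection and patients are unaffected. Occasional disagreement between test and interval (about 0.7% of trials in the simulations) would remain, so the text should also say that the CMH test decides.
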